FLUS can diagnose COVID-19 pneumonia with high sensitivity and specificity using PCR-test and chest radiograph as reference.

Aim

To study the ability of FLUS in COVID-19 to predictive respiratory failure.

To study the diagnostic capability of FLUS to find COVID-19 pneumonia.

To study risk-stratifying capability of FLUS in patients with COVID-19 symptoms.

Method

Design

Multicenter prospective cohort study with convenience sampling.

Setting

Emergency departments or internal medicine departments who admit patients with COVID-19 symptoms.

Participants

Patients who have COVID-19 symptoms and require diagnostic testing.

Patients who have a positive SAR-CoV-2 PCR-test and require admission to hospital.

Inclusion criteria

- Patients who are seen in COVID-clinics or emergency departments due to symptoms that require diagnostic work-up to COVID-19.
- Patients admitted to hospital with positive SARS-COV-2 PCR-test and in whom FLUS is performed less than 48 hours after admission.

Exclusion criteria

- Age less than 18 year.
- Former participation in this study.
- Pre-FLUS ventilator support.

Double inclusion

Inclusion in this study will not restrict patient from inclusion in other studies.

Recruitment

Participants are recruited at the local hospital. In Denmark the study is labelled quality assurance and the need for informed consent is thus waived. Local regulations are followed and it is the responsibility of each inclusion site to achieve appropriate regulatory permissions including need for approval from local ethical committees and healthcare authorities.

Variables

Ultrasound variables: FLUS are performed according to ERS guidelines and to Standard of Operating Procedure specific to this study. Film clips are recorded and saved for later evaluation. 14 zones are scanned. Film clips are marked with scanning position (L1, L2...etc.). If the patient is unable to sit, only anterior and lateral zones are scanned. FLUS findings are assessed on the film clips by an observer blinded to other variables. Findings are coded with 1/0 for presence of pneumonia. Moreover, a scoring system is applied:

FLUS findings	Score
Normal FLUS	0
Interstitial syndrome, defined as more than 3 B-lines in a single zone.	1
Diverse B-lines or irregular pleura	
Interstitial syndrome, defined as more than 3 B-lines in a single zone.	2
Confluent B-lines.	
Consolidations (sub-pleurale, lobar, with or without air-bronchograms)	3

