Data on FLUS operator: Level of medical degree. Years of experience with lung ultrasound. Completed training in FLUS.

From patient files the following data is extracted:

Patient demographic: Sex, age, height, weight, co-morbidities.

Clinical data on time of admission: Blood pressure, pulse, peripheral saturation, respiratory frequency, temperature, length of illness, list of symptoms, limitation to treatment i.e. not suited or willing to intensive care treatment and intubation.

Data from radiographic diagnostics: Result of chest radiograph, CT or HRCT scanning, if done for clinical reasons. No further review of radiographic examinations is performed. Results given by local radiology department is used.

Microbiological data: Result of SARS-CoV-2 PCR-test from nasal/oral/laryngeal or tracheal samples.

Data from admission: Time of admission. Place of admission. Time of dismissal. Admission to intensive care. Intubation. Time in ventilator. Death, survival. In hospital survival, 14- and 30-days survival.

Endpoints

Primary endpoint: FLUS (binary: positive/negative pneumonia) related to intubation (yes/no).

Secondary endpoints: Relationship between FLUS and SARS-CoV-2 PCR result.

Relationship between FLUS and radiographic findings.

Relationship between FLUS and admission to intensive care (not intubation).

Relationship between FLUS and re-admission (Patient returning to emergency department or COVID-clinic).

Scores of FLUS findings in different zones.

Data management

The study uses convenience sampling as FLUS may not be available at all times. FLUS is performed by the clinician such that only doctors with clinically relevant work are allowed to scan the patient. This minimizes the risk of disease transfer to doctors and reduces the use of protection equipment.

Ultrasound film clips are recorded according to standard operating procedure. Film clips are stored securely, according to local legal regulations. All variables extracted from patient files are stored in an eCRF using REDCap supplied by Aarhus University Hospital.

Every site will have access to enter data in data capture instruments. Access to REDCap is managed by the project steering committee at Aarhus University Hospital.

Data analysis

All data are analyzed in Stata.

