Statistical analysis plan.

Study name: The use of Focused Lung Ultrasound in Patients Suspected of COVID-19.

8.April 2020

Descriptive data:		
Demographic	Age	Mean, sd
	Sex	% kvinder
	Weight	Mean, sd.
	Height	Mean, sd.
	Site	groupe
Baseline data	BT sys	Mean, sd.
	BT dia	Mean, sd.
	SAT	Mean, sd.
	Puls	Mean, sd.
	Respiratory Rate	Mean, sd.
	Oxygen, l/min	Mean, sd.
	ferritin	Mean, sd.
	Hbg	Mean, sd.
	Leukocytter	Mean, sd.
	Lymfocytter	Mean, sd.
	Mono	Mean, sd.
	Neutrofile	Mean, sd.
	Egfr	Mean, sd.
	Karbamid	Mean, sd.
	Kreatinin	Mean, sd.
	Natrum	Mean, sd.
	Kalium	Mean, sd.
	Ddimer	Mean, sd.
	Probnp	Mean, sd.
	Tnt	Mean, sd.
	Tni	Mean, sd.
	glucose hba1c	Mean, sd.
	ph	Mean, sd.
	pco2	Mean, sd.
	po2	Mean, sd.
	be	Mean, sd.
	bicarbonat	Mean, sd.
	lactat	Mean, sd.
	Rtg af thorax	Grupper
	CT thorax	Grupper
	Covid-19 pcr	Yes/No
Treatment data	Antibiotica	Yes/No
	Antiviral	Yes/No

	Biological	Yes/No	
	Anti thrombotic	Yes/No	
	Death during admission	Yes/No	
	Length of admission	kontinuert	
	Death at 30 days	Yes/No	
	Cause of death	Covid/ikke-covid	
	Treatment restrictions, ITA	Yes/No	
	Treatment restrictions, ventilator	Yes/No	
FLUS data.	L1	0-3	
	L2	0-3	
	L3	0-3	
	L4	0-3	
	L5	0-3	
	L6	0-3	
	L7	0-3	
	R1	0-3	
	R2	0-3	
	R3	0-3	
	R4	0-3	
	R5	0-3	
	R6	0-3	
	R7	0-3	
	Flus mean	0-3, sd	
Inter- intraobservatør agreement			
Limits of agreement. Bland altmann.		20% Flus film re-scored by 1.observatør	Weigthed kappa kap s1 s2, tab wgt(w)
		20% Flus film scored by 2.observatør	Weigthed kappa kap o1 o2, tab wgt(w)
Mean Flus score related to event:			
Covid death	Parametric distribution qq plot and histogram		
	Norm +	t-test.	ttest flusmed, by(covdod)
	Norm -	Wilcoxon	ranksum flusmed, by(covdod)
			by covdod, sort : summarize flusmed, d graph bar (Mean) flusmed, over(covdod)
ITA admission	Parametric distribution qq plot and histogram		
	Norm +	t-test.	ttest flusmed, by(ita_in)
	Norm -	Wilcoxon	by ita_in, sort : summarize flusmed, d ranksum flusmed, by(ita_in)

			graph bar (Mean) flusmed, over(ita_in)
Ventilator treatment	Parametric distribution qq plot and histogram		
	Norm +	t-test.	ttest flusmed, by(respirator_beh)
	Norm -	Wilcoxon	by respirator_beh, sort : summarize flusmed, d ranksum flusmed, by(respirator_beh) graph bar (Mean) flusmed, over(respirator_beh)
Prædiction of event			
Covid death	Univariat logistical regression	Variable: covdod flusmed	
	Multivariate logistical regression	Variable: covdod, Flusmed, alder, køn, sat, ilt (kategori?)	

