ITA admission	Univariat logistiscal regression	Variable: ita_in flusmed	
	Multivariate logistical regression	Variable: ita_in, Flusmed, alder, køn, sat	, if behandlingsloft_ita ==0
Ventilator treatment	Univariat logistical regression	Variable: respirator_beh flusmed	
	Multivariate logistical regression	Variable: respirator_beh Flusmed, alder, køn, sat	, if behandlingsloft_resp ==0

Continuous variables are assessed for parametric distribution with quartile-quartile plots. Medians, interquartile ranges or means and standard deviations and ranges are reported according to parametric distribution. Students' t-test or Mann-Whitney U test is used as it was considered appropriate to evaluate differences between groups. The statistical significance is set to 5%. All data are handled in Excel (Microsoft) and REDCap (hosted at Aarhus University). All analyses are performed using Stata 14.2 (StataCorp, USA).

Building Prediction Models

Prediction models are based on multivariable logistic regression and preselected variables. The variables are sex, age, relevant comorbidity, oxygen administration and the mean-FLUS score. The selection of these variables is based on published data and clinical experience available to the study group during the study design stage. Explanatory variables are examined to decide cut-points, scales or the need for transformation. Variables are limited and prioritized to avoid overfitting or underfitting, respecting the study population size. Every included variable require at least 15 events.

The dependent variable is the primary outcome of interest: the COVID-19-related need for mechanical ventilation in the main analysis. Secondary outcomes are analyzed using the same logistic regression model, except for the outcome on high-flow oxygen treatment. The explanatory variable on oxygen administration is considered closely related to the outcome and is thus excluded from this analysis.

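### Patients already in intensive care or on high-flow oxygen when scanned can count as events that FLUS predicts, for these two secondary outcomes only

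*Protocol*

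**What the plan says.** **Eligibility.** Under Exclusion criteria, the one item on respiratory status is "Pre-FLUS ventilator support". Under Inclusion criteria, the second route admits "Patients admitted to hospital with positive SARS-COV-2 PCR-test and in whom FLUS is performed less than 48 hours after admission". The first route takes patients attending COVID-clinics or emergency departments for diagnostic work-up and sets no time window. The Setting section names "Emergency departments or internal medicine departments who admit patients with COVID-19 symptoms".

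**Outcomes.** The protocol's Endpoints section gives "Primary endpoint: FLUS (binary: positive/negative pneumonia) related to intubation (yes/no") and, among the secondary endpoints, "Relationship between FLUS and admission to intensive care (not intubation"). The SAP compares the mean FLUS score between patients with and without intensive care admission, using "ttest flusmed, by(ita_in") or the rank-sum equivalent, and then fits logistic models for the same outcome. The only restriction on the multivariable intensive care model is that the patient has no treatment limitation for intensive care. High-flow oxygen appears once, under Building Prediction Models, where secondary outcomes use the same regression "except for the outcome on high-flow oxygen treatment". For that outcome the oxygen covariate is removed.

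**Timing data.** The protocol's Variables section lists "Data from admission: Time of admission. Place of admission. Time of dismissal. Admission to intensive care. Intubation. Time in ventilator". It names no time for the scan, for intensive care admission or for the start of high-flow oxygen.

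**The concern.** The stated aim is to predict respiratory failure, and the SAP groups these models under prediction of events. A patient who has already reached the outcome cannot have it predicted. In that patient the scan describes current severity.

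Patients already in intensive care or on high-flow oxygen are likely to be sicker and more often FLUS-positive than the rest. Including them as events therefore pushes the association upwards. The plan handles this correctly for ventilation by excluding patients ventilated before the scan, but it does not carry the principle over to the other two outcomes. For high-flow oxygen, dropping the oxygen covariate means that oxygen treatment at the scan is neither an exclusion nor an adjustment.

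At stake is the interpretation of two secondary results, which could mix diagnosis of present severity with prediction.

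**Working it through.** **The plan's own figure.** The sample size concerns intubation: 75 events / 0.20 = 375 patients, the lower end of the stated 375-400. At 400 patients the same rate gives 80 events. The documents give no figure for patients already in intensive care or on high-flow oxygen at the scan, so the size of the problem can only be shown under assumptions.

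**Which outcomes are exposed.**
- Intubation or ventilation: patients ventilated before FLUS are excluded. A patient in intensive care or on high-flow oxygen but not ventilated is still validly at risk. Not exposed.
- Intensive care admission: no exclusion and no timing rule. Exposed through the 48-hour route in particular.
- High-flow oxygen: no exclusion, no timing rule and no oxygen covariate. Exposed.

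**Assumptions for intensive care.** N = 400 (upper end of the protocol's range). A share f is already in intensive care at the scan, and 15% of the remainder are admitted later, unrelated to FLUS. FLUS is positive in 80% of those already there and in 50% of everyone else. The test is the protocol's chi-square on binary FLUS at 5%.

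**Formulas.**
- Share of events that precede the scan: a = f / (f + 0.15 × (1 − f)).
- FLUS-positive proportion among all events: p = 0.80a + 0.50(1 − a).
- Odds in non-events are 0.5/0.5 = 1, so the odds ratio is p / (1 − p).

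For f = 5%: a = 0.05 / (0.05 + 0.1425) = 0.260; p = 0.208 + 0.370 = 0.578; OR = 0.578 / 0.422 = 1.37.

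| Already in intensive care (of 400) | Share of events before scan | OR, true OR 1 | Chi-square rejects | OR, true OR 3 |
|---|---|---|---|---|
| 0.5% (2) | 3% | 1.04 | about 5% | 3.03 |
| 1% (4) | 6% | 1.08 | about 6% | 3.05 |
| 3% (12) | 17% | 1.23 | about 12% | 3.14 |
| 5% (20) | 26% | 1.37 | about 23% | 3.22 |

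Rejection rates come from simulation, with at least 20,000 data sets per row. The last column replaces 0.50 by 0.75 for later admissions (odds 3, so a true OR of 3). For f = 5%: p = 0.260 × 0.80 + 0.740 × 0.75 = 0.763, OR = 3.22.

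**Sensitivity to the assumed FLUS positivity.** Take 375 patients and 75 events (the 20% intubation rate, borrowed), FLUS positive in 60% of non-events and in 95% of events already present. If 10%, 25% or 50% of events precede the scan, a true OR of 1 becomes 1.16, 1.47 or 2.30, and a true OR of 2 becomes 2.23, 2.67 or 3.78. For 10% and a true OR of 1: p = 0.9 × 0.60 + 0.1 × 0.95 = 0.635; OR = (0.635/0.365) / 1.5 = 1.16. The direction is the same. The size depends on the share of events present at the scan and on how strongly FLUS marks them.

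No calculation was made for high-flow oxygen. The documents give neither its frequency nor the share already receiving it.

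**The case against.** The strongest reply is that few patients would be affected. Recruitment is in emergency and internal medicine departments, one of the two inclusion routes is diagnostic work-up, and a problem case must be admitted, in intensive care, not ventilated, and scanned inside the window. At 0.5% to 1% the effect is negligible. This stands for intensive care, as a statement about likely size. It does not remove the gap, because the Setting line is not an eligibility rule and does not limit high-flow oxygen started on a ward before the scan.

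It is also fair to say that the false-rejection figures assume no true relation between FLUS and later admission, which is where the distortion looks worst. They also apply to the chi-square on binary FLUS. The SAP uses the mean score and adjusted regression, where saturation or oxygen may absorb part of current severity, so the rates do not transfer directly. High-flow oxygen is not a protocol endpoint and has no row in the SAP's outcome table.

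Some collected items could help. Place of admission might show direct admission to intensive care, and baseline oxygen in l/min might identify some patients already on high flow. Neither is tied to a rule in the analysis.

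A reader might infer two stronger things. One is that the primary result is contaminated; the exclusion of ventilated patients rules that out. The other is that such patients are known to have been counted, or that a 23% false-positive rate is to be expected. The documents show only that nothing prevents it, and 23% requires about a quarter of intensive care events to precede the scan.

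**Conclusion.** The concern holds for intensive care admission and high-flow oxygen, both secondary. As written, the analysis lets events that came before the scan count as predicted by it. This is a biased rule, not merely a missing detail, and it is cheap to correct. The primary analysis is unaffected.

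The likely size is unknown. For intensive care it runs from negligible, if 1% or fewer are already there, to an odds ratio of 1.37 under no true effect at 5%. With a true odds ratio of 3, the shift is to at most about 3.2 over the same range. These limits rest on the assumed 80% FLUS positivity among those already in intensive care and would widen if it were higher. For high-flow oxygen the argument is one of design only, without a figure.

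**What to change.** In the SAP, define intensive care admission and high-flow oxygen each as the first occurrence after the FLUS time. Restrict each analysis to patients free of that state at the scan, and report the number left out. Apply this to the group comparisons for intensive care as well as to the regression models. Patients left out of one of these analyses stay in the primary analysis.

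In the eCRF, record the date and time of FLUS, of intensive care admission and of high-flow start, taken from patient files. Scan timing must be known in any case to apply the 48-hour criterion.

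The cost is a few extra data fields and somewhat fewer events for these two outcomes. Under the assumptions above with 400 patients, intensive care events fall from about 63 to 59 at 1% already present (4 + 0.15 × 396 against 0.15 × 396) and from 77 to 57 at 5% (20 + 0.15 × 380 against 0.15 × 380). The number of variables that the SAP's minimum of 15 events each allows should be checked against the reduced count.

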Focused lung ultrasound for diagnosing and risk- stratification of patients with COVID-19 symptoms

April 8, 2020
NCT 04327674

Background

COVID-19 is defined as an infectious disease caused by SAR-CoV-2 virus. It results in pneumonia and sometimes respiratory failure. SARS-CoV-2 pandemic has led to massive strain on health care facilities. A large proportion of the population is at risk of COVID-19 and some estimates suggest that up to 15% will need hospitalization. Such number of patients strains the health care system to its maximum as capacity has limitations even in highly developed countries.

Early reports estimate that more than 80% of patients admitted to hospital with COVID-19 have abnormal findings on chest radiographs¹. Thus, imaging seems to be an important part of the diagnostic work-up. In most hospitals however, access to CT-scanning of the thorax of all patients with COVID-19 or with suspicion of COVID-19 is unrealistic due to restricted capacity. Chest radiographs are faster and easier to do, but may require transportation of the patient to the department of radiology which carries a risk of virus spreading in the hospital. On-site chest radiograph is often of such low quality that diagnosis or follow-up will be difficult.

Focused ultrasound examination of the lungs, FLUS, is a diagnostic tool that can show changes in the lung parenchyma due to pneumonia. FLUS is a bed-side examination performed by the physician which results in reduced risk of in-hospital virus contamination. Furthermore, results from FLUS are immediately available to the physician. This allows rapid decision-making which is essential in cases of high patient burdens as seen in the COVID-19 pandemic.

Furthermore, SARS-CoV-2 positive patients with pneumonia may be at higher risk of respiratory failure than those without pneumonia. Identifying patients at high risk can qualify decisions about monitoring level and organization of intensive care resources. Conversely, patient with COVID-19 symptoms but without pneumonic FLUS finding could likely be managed as out-patients. Such a risk-stratification may optimize the allocation of limited healthcare resources and reserve in-hospital capacity to those patients who needs it.

Hypothesis

FLUS can risk-stratify patients with COVID-19 symptoms.

FLUS can predict respiratory failure in patients with COVID-19 pneumonia.

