Binary endpoints, including primary endpoint, are analyzed using Chi-2 test. Continuous data are assessed for parametric distribution and analyzed with Student's T-test on logarithmic transformed data in case of non-parametric distribution.

Level of statistical significance is set to 5%.

A logistic prediction model will be developed. Dependent variable is intubation. Independent variables are age (continuous), FLUS result (Binary or ordinal), SARS-CoV-2 status (Binary) and peripheral oxygen saturation (continuous).

The data set will be divided in two. One is used for model development and one is used for validation of the model. Geographic external validity is tested. Internal validity is tested with bootstrapping method. Sensitivity, specificity and ROC AUC is calculated.

Sample size

No prior publications are available for sample size estimation.

For the prediction model we wish to include 10-15 events per independent variable, 50-75 events. From early estimations about 20% of admitted patients requiring intubation our estimate is 375-400 participants.

Inclusion period

An end date is set to May 15 2020. If COVID-19 pandemic is ongoing at this time point the study may extent.

Blinding

Ultrasound film clips are analyzed blinded to other variables.

Plan for publication

Data analysis is estimated to end July 1. 2020. Article submission is estimated to October, 2020.

Preliminary data analysis

Available data will be analyzed soon after 15. May.

Ethical considerations

FLUS is without any risk to patients. COVID-19 is an infectious disease and isolation is needed. Contamination during the study needs to be avoided. For this reason, FLUS is only performed by the physicians who are required to see the patient regardless of this study. The ultrasound equipment is cleaned after each examination in accordance with local guidelines.

Legal regulations

In Denmark the study is classified as a quality assurance project. Arrangements and permission to access to patient files in each site is required. According to guidance from the legal office at Region Midt a data management agreement is not needed.

International data agreements are required to data transfer from international sites to Denmark.

All international sites must adhere to local regulation. Responsibility of this is on the international site.

Publication

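### Sensitivity and specificity of FLUS against chest radiograph would come only from patients imaged for clinical reasons, and the SAP does not say how patients without imaging are handled

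*Protocol*

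**What the plan says.** The protocol's Hypothesis section states: "FLUS can diagnose COVID-19 pneumonia with high sensitivity and specificity using PCR-test and chest radiograph as reference". Under Endpoints, "Relationship between FLUS and radiographic findings" is a secondary endpoint.

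The Variables section takes the imaging reference from patient files: "Result of chest radiograph, CT or HRCT scanning, if done for clinical reasons". The local report is used as it stands: "No further review of radiographic examinations is performed".

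On who scans, Data management says "FLUS is performed by the clinician such that only doctors with clinically relevant work are allowed to scan the patient". The Background says that "results from FLUS are immediately available to the physician", and suggests that a "patient with COVID-19 symptoms but without pneumonic FLUS finding could likely be managed as out-patients".

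The FLUS result that enters the analysis is a later reading of the stored clips by an observer blinded to the other variables (Variables; Blinding).

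For analysis, the protocol says "Binary endpoints, including primary endpoint, are analyzed using Chi-2 test". It names sensitivity, specificity and ROC AUC only in the paragraph on the intubation prediction model. The SAP lists chest radiograph and CT as descriptive rows. It sets out no analysis of FLUS against imaging and no handling of patients without imaging.

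**The concern.** A study of diagnostic accuracy needs the reference result in everyone, or in a subset chosen independently of the index test and of disease. Here the reference exists only where a clinician wanted the image. The clinician who scanned may have had the FLUS impression in mind, and sicker patients are likelier to be imaged whatever the scan shows. With no rule for unimaged patients, the default is a complete-case comparison, which is open to partial-verification bias.

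At stake is the diagnostic-accuracy claim in the Hypothesis section. A published sensitivity or specificity could partly describe who was sent for imaging rather than how well FLUS detects pneumonia.

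**Working it through.** **Inputs.** The documents give no imaging rates, no expected accuracy and no prevalence of radiographic pneumonia. The only planning figure is for the intubation model: 75 events / 0.20 = 375 participants, which reproduces the lower end of the stated 375-400. It does not bear on accuracy against imaging. Everything below is therefore an assumption, shown over a range.

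**1. Imaging depends on FLUS only.** Let se and sp be the true values, and v1 and v0 the shares imaged among FLUS-positive and FLUS-negative patients.

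- Apparent sensitivity = se·v1 / [se·v1 + (1−se)·v0]
- Apparent specificity = sp·v0 / [sp·v0 + (1−sp)·v1]

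With se = sp = 0.80, v1 = 0.90 and v0 = 0.40, sensitivity is 0.72/(0.72 + 0.08) = 0.90 and specificity is 0.32/(0.32 + 0.18) = 0.64. Prevalence drops out.

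| Imaged, FLUS+ / FLUS− | Apparent sensitivity | Apparent specificity |
|---|---|---|
| 90% / 90% | 80.0% | 80.0% |
| 90% / 60% | 85.7% | 72.7% |
| 80% / 50% | 86.5% | 71.4% |
| 90% / 40% | 90.0% | 64.0% |
| 90% / 30% | 92.3% | 57.1% |
| 50% / 90% | 69.0% | 87.8% |

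With 90% of FLUS-positive patients imaged and the FLUS-negative share falling from 90% to 30%, the bias runs from 0 to +12 points in sensitivity and 0 to −23 points in specificity. At true values of 0.90 and 0.70 the same range gives 0 to +6 and 0 to −26. The last row shows the reversal.

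**2. The association test.** In the full cohort the odds ratio is (0.80 × 0.80)/(0.20 × 0.20) = 16. Among imaged patients, v1 and v0 each appear once in the numerator and once in the denominator, so they cancel and the odds ratio stays 16. If imaging depends on FLUS alone, the association examined by the Chi-2 test is not distorted. Sensitivity and specificity are.

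**3. Imaging also depends on severity.** Take 400 patients, 50% with radiographic pneumonia, se = sp = 0.80, and severe illness in 70% of those with pneumonia and 20% of those without. Image 90% of everyone except non-severe FLUS-negative patients, of whom 30% are imaged.

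- True positives: 160, imaged 144.
- False negatives: 40 (28 severe, 12 not), imaged 25.2 + 3.6 = 28.8.
- False positives: 40, imaged 36.
- True negatives: 160 (32 severe, 128 not), imaged 28.8 + 38.4 = 67.2.

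Complete case: sensitivity 144/172.8 = 0.833; specificity 67.2/103.2 = 0.651. The odds ratio is now (144 × 67.2)/(36 × 28.8) = 9.3 rather than 16, so the protection in step 2 is lost.

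Begg-Greenes on FLUS alone: the 200 FLUS-positive patients are assigned 200 × 144/180 = 160 with pneumonia, and the 200 FLUS-negative patients 200 × 28.8/96 = 60. Sensitivity is 160/220 = 0.727 and specificity 140/180 = 0.778. Sensitivity is further from 0.80 than without correction.

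Begg-Greenes on FLUS and severity: the FLUS-negative group is assigned 60 × 25.2/54 = 28 plus 140 × 3.6/42 = 12, that is 40. Sensitivity is 160/200 = 0.80 and specificity 160/200 = 0.80. Both are recovered, because in this example nothing else drives imaging.

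**The case against.** A reader might infer that the scanning physician orders the imaging with the FLUS result in hand, so that sensitivity is overstated and specificity understated. The documents do not support that much. No section says who orders imaging or that it follows FLUS. Admitted patients may be scanned up to 48 hours after admission, so some may be imaged first, and the order of the two is not a listed variable. The remark about immediate results is general background. The direction is open too: the Background presents FLUS as a way round scarce imaging and patient transport, so a positive scan might replace a radiograph. These points stand, and they make the mechanism an inference and the direction unknown. They do not remove selection by clinical severity, which can operate whatever the order.

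It can also be said that the endpoint is only a relationship tested by Chi-2, which FLUS-dependent imaging leaves intact. That holds when imaging depends on FLUS alone. It does not cover the Hypothesis section, which names sensitivity and specificity against chest radiograph.

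A further tempting reading is that a correction from data already collected removes the bias. It may not. Ordering would follow the bedside impression, which is not a listed variable; the blinded clip reading is only a proxy. Nor does a correction repair unreviewed local reports or the on-site radiographs that the Background describes as often poor.

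**Conclusion.** The point holds in a conditional form. Sensitivity and specificity of FLUS against chest radiograph, computed in imaged patients alone, may be biased because imaging is selective and may depend on FLUS or on severity. In the assumed scenarios with true values of 80% and 80%, the error reaches about 12 points in sensitivity and 23 in specificity when FLUS-positive patients are imaged more often. It takes the opposite sign when they are imaged less often, and is zero with equal rates and no other selection. All of this rests on assumed imaging rates and accuracy.

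The primary endpoint does not use imaging and is unaffected. This is an inexpensive improvement to a secondary analysis, not a flaw in the main result.

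**What to change.** Add to the SAP:

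1. A table of the number and share imaged by FLUS result. This shows whether imaging differed by FLUS at all.
2. A statement that uncorrected sensitivity and specificity apply to imaged patients only.
3. A sensitivity analysis, printed next to the uncorrected figures, using inverse-probability-of-imaging weights or Begg-Greenes stratified on FLUS plus recorded severity. The variables are FLUS result, saturation, respiratory rate, temperature, PCR result and site. Correction on FLUS alone should be ruled out, for the reason shown in step 3 of the working.
4. A range for unrecorded selection, for example by letting the odds of radiographic pneumonia in unimaged patients differ from those in imaged patients with the same recorded values.

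The cost is SAP wording and one additional analysis; no extra imaging is needed. The confidence intervals will be wider, and the corrected estimate assumes that imaging depends only on recorded variables. Because the clip reading only approximates the bedside impression, the report should say that some bias may remain.
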